Post-authorisatiannexon Safety Study Protocol: Besremi-PASS

Title	A Prospective, Multicentre, Non-interventional, Observational, Post-authorisation Safety Study of Ropeginterferon alfa-2b in Polycythaemia Vera Patients		
Protocol version identifier	Besremi-PASS		
Date of last version of protocol	25APR2019		
EU PAS register number	EUPAS29462		
Active substance	Active substance: Ropeginterferon alfa-2b Pharmacotherapeutic group: Immunostimulants, interferons, ATC code: L03AB15		
Medicinal product	Besremi 250 micrograms/0.5 mL solution for injection in pre-filled pen Besremi 500 micrograms/0.5 mL solution for injection in pre-filled pen		
Product reference	EU/1/18/1352/001 EU/1/18/1352/002		
Procedure number	EMEA/H/C/004128/0000		
Marketing authorisation holder	AOP Orphan Pharmaceuticals AG [name]		
Joint PASS	No		
Research question and objectives	The objective of the study is to provide further data to characterize the safety and tolerability of ropeginterferon alfa-2b by monitoring the hepatic and cardiovascular safety in patients with polycythaemia vera treated with ropeginterferon alfa-2b in routine post-authorisation use.		
Countries of study	Austria (approx. 10 sites) and Germany (approx. 15 sites)		
Author & MAH contact person			

1. Table of contents

1. Table of contents	2
2. List of abbreviations	3
3. Responsible parties	4
4. Abstract	5
5. Amendments and updates	7
6. Milestones	7
7. Rationale and background	7
8. Research question and objectives	
9. Research methods	9
9.1. Study design	9
9.2. Setting	10

11.1 Definitions	
11.2 Documentation of AEs	25
11.3 Management and reporting of AEs/ADRs	26
12. Plans for disseminating and communicating study results	27
13. References	28
Annex 1. List of stand-alone documents	29
Annex 2. ENCePP checklist for study protocols	30
Annex 3. Additional information	31

2. List of abbreviations

ADL Activities of Daily Living ADR Adverse Drug Reaction

AE Adverse Event

ALT Alanine Aminotransferase

ATC Anatomical Therapeutic Chemical AST Aspartate Aminotransferase

CA Competent Authority
CI Confidence Interval

CTCAE Common Terminology Criteria for Adverse Events

DILI Drug Induced Liver Injury

DM Data Management EC Ethics Committee CRF Case Report Form

eCRF Electronic Case Report Form
EMA European Medicines Agency
FAS Full Analysis Data Set
GCP Good Clinical Practice
GDocP Good Document Practice

GVP Guideline on Good Pharmacovigilance Practice

Gamma-Glutamyl Transferase

Hb Haemoglobin

GGT

ICF Informed Consent Form

ICH International Council for Harmonisation

IFN Interferon

IME Important Medical Event ISF Investigator Site File

MACE Major Adverse Cardiac Events
MAH Marketing Authorisation Holder

MedDRA Medical Dictionary for Regulatory Activities

MP Medicinal Product

PIC Patient Identification Code
PIL Patient Information Leaflet

PPS Per Protocol Dataset

PSMF Pharmacovigilance System Master File

PSUR Periodic Safety Update Report

PV Polycythaemia Vera

PASS Post-authorisation Safety Study RSI Reference Safety Information

SAE Serious Adverse Event SAP Statistical Analysis Plan

STATA Validated statistical analysis software by Stata Corporation

SOC System Organ Class

SmPC Summary of Product Characteristics

ULN Upper Limit of Normal WHO World Health Organisation

3. Responsible parties

3.1. Authorized Representative (Signatory)/Responsible party

The name and contact information of all of the individuals involved with the study (e.g. coordinating Investigator for each country, a full list of all participating Investigators, medical director, authorized representative(s) of the MAH) will be maintained separately from the study protocol and be made available upon request.

4. Abstract

Title

A Prospective, Multicentre, Non-interventional, Observational, Post-authorisation Safety Study of Ropeginterferon alfa-2b in Polycythaemia Vera Patients

Protocol Version 2.0, dated 13SEP2019

Rationale and background

Ropeginterferon alfa-2b is indicated as monotherapy in adults for the treatment of polycythaemia vera without symptomatic splenomegaly.

AOP Orphan Pharmaceuticals AG committed to the European Medicines Agency (EMA) to conduct this post-authorisation observational safety study to gain additional information on the safety and tolerability of ropeginterferon alfa-2b in patients with polycythaemia vera, specifically to address the effectiveness of the risk minimisation measures for hepatotoxicity and to evaluate the cardiovascular safety.

Research question and objectives

"What is the incidence rate of the important, identified risk "hepatotoxicity" in PV patients newly treated with ropeginterferon alfa-2b in routine post-authorization use?"

The objective of this study is to provide further data to characterize the safety and tolerability of ropeginterferon alfa-2b by monitoring the hepatic and cardiovascular safety in patients with polycythaemia vera treated with ropeginterferon alfa-2b in routine post-authorisation use.

Study design

This is a prospective, multicentre, non-interventional, observational, post-authorisation safety study of ropeginterferon alfa-2b (250 micrograms or 500 micrograms solution for injection in pre-filled pen) in adult polycythaemia vera patients.

The study will be conducted in two parts for the assessment of safety:

- Part A: observation of patients during the first 6 months of ropeginterferon alfa-2b treatment for the evaluation of hepatotoxicity and major cardiovascular adverse events (interim analysis after 6 months)
- Part B: follow-up observation of patients for an additional 12 months of ropeginterferon alfa-2b treatment for further evaluation of hepatotoxicity and major cardiovascular adverse events

Patients who will be monitored in this study will receive ropeginterferon alfa-2b in the course of routine clinical practice. To be eligible for study inclusion, patients must meet all inclusion and none of the exclusion criteria.

The estimated study duration is approximately 3.5 years, from the first patient receiving ropeginterferon alfa-2b treatment (baseline) until the end of the observation time of the last patient within the study.

The observation time per patient in the study will be

- 6 months in Part A
- 12 months in Part B

The maximum study duration per patient will be 18 months.

Population

The study population will be adult polycythaemia vera patients. Ropeginterferon alfa-2b therapy will be in accordance with the physician's routine clinical practice (who is experienced in the management of polycythaemia vera) and with the recommendations in the current product information for ropeginterferon alfa-2b (Annex 1).

Variables

Parameters of the standard assessments will be monitored which include the collection of cardiovascular events [i.e. thromboembolic adverse events and major adverse cardiac events [MACE], treatment-emergent hepatobiliary adverse drug reactions, other treatment-emergent adverse events and clinical laboratory parameters (i.e. liver enzymes/bilirubin; haematocrit).

Data sources

Data will be collected from the medical records of the patients in the study.

Study size

Approximately 228 adult polycythaemia vera patients.

Data analysis

The safety dataset will contain all patients who were enrolled in this study, received ropeginterferon alfa-2b treatment at least once during routine medical setting and from whom data are available.

Milestones

The planned milestones are the final study protocol, start and end of data collection, interim and final report.

5. Amendments and updates

Number	Date	Section of study protocol	Amendment or update	Reason
1	13SEP2019	3, 4, 5, 6, 7, 8, 9, 11, 12	Specification of study objectives; specification of evaluation of risk minimization measures; change to duration of patient observation	PRAC Assessment report

6. Milestones

Milestone	Planned date
Study protocol	Q1/Q2 2019
Start of data collection (first patient in)	Q3 2019
End of data collection (last patient out)	Q1 2023
Interim report	Q1 2022
Final report of study results	Q3 2023

7. Rationale and background

Polycythaemia vera (PV), a myeloproliferative neoplasm, is a very rare disease and typically develops in late adulthood. It is an acquired form of primary erythrocytosis which is characterized by an excess production of erythrocytes, leukocytes and platelets.

Ropeginterferon alfa-2b belongs to the pharmacotherapeutic group of antineoplastic and immunostimulating agents, immunostimulants; interferons (IFNs). Ropeginterferon alfa-2b is the first IFN indicated as monotherapy in adults for the treatment of PV without symptomatic splenomegaly.

The general safety profile of ropeginterferon alfa-2b can be seen as well characterized and safety data provided for ropeginterferon alfa-2b can be compared with that of already approved IFN products.

Hepatic safety

Hepatotoxicity is a well-known safety class effect of IFNs¹ (including cases of drug-induced liver injury [DILI]) characterized by potentially significant increases in liver enzymes. Hepatotoxicity has to be considered as the most clinically relevant toxicity of IFNs, including also ropeginterferon alfa-2b.

¹ Hepatotoxicity is included as important, identified safety concern in the EMA approved Risk Management Plan for ropeginterferon alfa-2b (Version 1.0, dated 13DEC2018).

Increases in alanine aminotransferase (ALT) (≥ 3 times the upper limit of normal), aspartate aminotransferase (AST) (≥ 3 times the upper limit of normal), gamma-glutamyl transferase (GGT) (≥ 3 times the upper limit of normal) and bilirubin (> 2 times the upper limit of normal) levels have been observed in patients treated with ropeginterferon alfa-2b. These elevations were mostly transient and occurred during the first treatment year.

Cardiovascular safety

Thromboembolic events are rare events but appear significantly more frequent in PV patients than in the healthy population and are a major risk of this disease.

The recommended posology for the titration phase of ropeginterferon alfa-2b results in a prolonged time to reach the individual optimal dose compared to hydroxycarbamide. In a phase III clinical study in PV (PROUD-PV; EudraCT number 2012-005259-18), the end of the mean individual titration phase for ropeginterferon alfa-2b was reached after approximately 3.7 months, for hydroxycarbamide after approximately 2.6 months of treatment. Thus, other products (e.g. hydroxycarbamide) may be preferred in patients for whom an early reduction in elevated blood counts is necessary to prevent thrombosis and bleeding. During the titration phase the effectiveness to reduce the cardiovascular and thromboembolic risk of the underlying disease may not be fully established.

Risk minimization measures for the important, identified risk of "hepatotoxicity"

The routine risk communication in the Summary of Product Characteristics (SmPC) and Patient Information Leaflet (PIL) and legal status (prescription only medicine) implemented in the EMA approved Risk Management Plan for ropeginterferon alfa-2b (Version 1.0, dated 13DEC2018) are considered sufficient to manage the important identified risk "hepatotoxicity".

Evaluation of the effectiveness of risk minimization measures for the important, identified risk "hepatotoxicity" during this post-authorization safety study will focus on the risk communication in the SmPC. Specifically, on the recommendations on hepatic enzyme monitoring during long-term treatment with ropeginterferon alfa-2b and dose adjustments (including dose changes or treatment discontinuation) in case of adverse events.

8. Research question and objectives

In addition to the routine pharmacovigilance activities, AOP Orphan Pharmaceuticals AG proposed to the EMA to conduct this post-authorization safety study to address the effectiveness of the risk minimization measures for the important, identified risk of hepatotoxicity and to evaluate the cardiovascular safety within the cohort of patients with PV and treated with ropeginterferon alfa-2b.

The main research question is: "What is the incidence rate of the important, identified risk "hepatotoxicity" in PV patients newly treated with ropeginterferon alfa-2b in routine post-authorization use?"

1. Primary objective

• To assess the incidence rate of the important, identified risk "hepatotoxicity" in PV patients newly treated with ropeginterferon alfa-2b in routine post-authorization use.

2. Secondary objectives

- To describe the baseline characteristics of PV patients newly treated with ropeginterferon alfa-2b in routine post-authorization use.
- To evaluate the effectiveness of the risk minimization measures for the important, identified risk "hepatotoxicity".

- To further characterize the important, identified risk "hepatotoxicity" in subgroups of the patient population (i.e. with/without co-medication with nonsteroidal anti-inflammatory drugs, with/without pre-existing liver disease or baseline liver parameter elevation).
- To assess the incidence rate of thromboembolic adverse events and major adverse cardiac events (MACE) in PV patients newly treated with ropeginterferon alfa-2b in routine post-authorization use.
- To further evaluate cardiovascular safety in subgroups of the patient population (i.e. with/without cardiovascular risk factors, with/without pre-existing cardiovascular disease).

9. Research methods

9.1. Study design

This is a prospective, multicentre, non-interventional, observational, post-authorization safety study of ropeginterferon alfa-2b in adult PV patients.

The purpose of the study is to conduct analyses of safety data related to ropeginterferon alfa-2b treatment. The study will be conducted in two parts over 18 months for the assessment of safety:

- Part A: observation of patients during the first 6 months of ropeginterferon alfa-2b treatment for the evaluation of hepatotoxicity and major cardiovascular adverse events (interim analysis after 6 months)
- Part B: observation for an additional 12 months of ropeginterferon alfa-2b treatment for the evaluation of hepatotoxicity and major cardiovascular adverse events

Participation will be offered to patients who receive ropeginterferon alfa-2b in the frame of clinical routine. Due to the non-interventional nature of this study, the decision to prescribe ropeginterferon alfa-2b is clearly separated from inclusion.

Ropeginterferon alfa-2b therapy will be in accordance with the physician´s routine clinical practice (who is experienced in the management of PV) and with the recommendations in the product information for ropeginterferon alfa-2b (Annex 1).

Safety endpoints:

- Liver enzymes (i.e. ALT, AST, GGT), and bilirubin
- Cardiovascular events (thromboembolic adverse events and major adverse cardiac events [MACE])
- Treatment-emergent hepatobiliary adverse drug reactions
- All treatment-emergent adverse events

Evaluation of effectiveness of risk minimization measurements for the important, identified risk "hepatotoxicity":

The effectiveness of the recommendation to monitor hepatic enzymes during long-term ropeginterferon alfa-2b treatment as described in section 4.4 of the SmPC will be evaluated by assessing the frequency of hepatic enzyme and bilirubin evaluation in routine clinical practice.

The effectiveness of the routine risk communication to address dose adjustment or treatment discontinuation in case of hepatotoxicity, as described in section 4.2 and 4.4 of the SmPC, will be evaluated by assessing rate of dose adjustments or treatment discontinuations due to hepatoxicity, the rate of hepatobiliary adverse events occurring despite dose reduction or treatment discontinuation due to elevated liver enzymes, the rate of, and time to resolution of significant elevations of ALT, AST, GGT (≥3 times ULN) and/or bilirubin (> 2 times ULN) and/or hepatobiliary adverse drug reactions as well as the number of patients experiencing

hepotobiliary adverse events after significant elevations of liver enzymes ALT, and/or AST, and/or GGT (≥3 times ULN) and/or bilirubin (>2 times ULN).

Endpoints for the evaluation of effectiveness of risk minimization measurements for the important, identified risk "hepatotoxicity":

- Evaluations of liver enzymes (i.e. ALT, AST, GGT), and bilirubin in routine clinical practice
- Hepatobiliary adverse events after dose reduction or treatment discontinuation due to elevated liver enzymes
- Dose reduction or treatment discontinuation due to hepatotoxicity
- Liver enzymes (i.e. ALT, AST, GGT), and bilirubin after dose reduction or treatment discontinuation
- Treatment-emergent hepatobiliary adverse drug reactions after dose reduction or treatment discontinuation
- Number of patients with hepatobiliary adverse events after significant elevations of liver enzymes ALT, and/or AST, and/or GGT (≥3 times ULN) and/or bilirubin (>2 times ULN)

9.2. Setting

Due to the start of commercialization of Besremi in Austria and Germany, this postauthorization safety study will be conducted in approximately 10 sites in Austria and 15 sites in Germany.

9.2.1 Medicinal Product (MP)

The MP for this study is ropeginterferon alfa-2b (Besremi). Ropeginterferon alfa-2b is licensed as 250 micrograms or 500 micrograms solution for injection in a pre-filled pen. The Investigator will record the MP lot number(s) in the eCRF. Administration, packaging, labelling, and storage for the MP are described in the product information for ropeginterferon alfa-2b (Annex 1).

9.2.1.1 Ropeginterferon alfa-2b treatment phases

Titration phase

The ropeginterferon alfa-2b dose is titrated individually with a recommended starting dose of 100 micrograms (or 50 micrograms in patients under another cytoreductive therapy). The dose should be gradually increased by 50 micrograms every two weeks (in parallel, other cytoreductive therapy should be decreased gradually, as appropriate) until stabilisation of the haematological parameters is achieved (haematocrit <45%, platelets <400 x 10^9 /L and leukocytes <10 x 10^9 /L). The maximum recommended single dose is 500 micrograms injected every two weeks.

Maintenance phase

The ropeginterferon alfa-2b dose at which stabilisation of the haematological parameters is achieved should be maintained in a two-week administration interval for at least 1.5 years. After that, the dose may be adapted and/or the administration interval prolonged up to every four weeks, as appropriate for the patient.

Detailed information on the recommended posology and method of administration can be found in the product information for ropeginterferon alfa-2b (Annex 1).

9.2.1.2 MP (ropeginterferon alfa-2b) complaints

Any complaints and queries (e.g. wrong strength/labelling, malfunction of devices, faulty closure, empty vial) concerning the MP have to be reported by the Investigator to the Sponsor immediately by sending an e-mail to [contact].

9.2.2 Duration of Study Period(s) and Subject Participation

The overall duration of the study is expected to be approximately 3.5 years from study initiation (i.e. first patient receiving ropeginterferon alfa-2b treatment within the study [first patient in]) to study completion (i.e. the end of the observation time of the last patient within the study [last patient out]). The recruitment period is expected to be approximately 2 years.

The individual patient participation is a maximum of 18 months (6 months in Part A and 12 months in Part B)

9.2.3 Study population

Participation will be offered to patients who receive ropeginterferon alfa-2b in the frame of clinical routine and according to its approved labeling. Due to the non-interventional nature of this study, the prescription of ropeginterferon alfa-2b must be separated from the decision to include a patient into this study.

9.2.3.1 Inclusion and exclusion criteria

The study will include approximately 228 adult PV patients. The inclusion and exclusion criteria are listed below.

• Inclusion criteria:

- 1. Patients who receive ropeginterferon alfa-2b in the frame of clinical routine and according to its approved labelling: monotherapy in adults (≥ 18 years old) for the treatment of PV without symptomatic splenomegaly and according to the recommendations in the product information for ropeginterferon alfa-2b (Annex 1)
- 2. Patient's medical history is available
- 3. Patient provides written informed consent prior to study entry

• Exclusion criteria:

- 1. Patients with any contraindication to ropeginterferon alfa-2b treatment according to the product information for ropeginterferon alfa-2b (Annex 1)
- 2. Patients involved in any study with another investigational product or therapy (in the prior 30 days)
- 3. Previous ropeginterferon alfa-2b treatment
- 4. Patient is a family member or employee of the Investigator

9.2.3.2 Pregnancy and lactation

Women of childbearing potential/contraception in females

Women of childbearing potential have to use effective contraception during the treatment with ropeginterferon alfa-2b, unless otherwise discussed with the Investigator.

According to product information, ropeginterferon alfa-2b is not recommended during pregnancy and during breast-feeding (Annex 1).

9.2.4 Informed consent and enrolment

Any volunteer who provides informed consent (i.e. signs and dates the informed consent form) is considered enrolled in the study (Section 10.5).

² PV disease history, cardiovascular risk-factors, pre-existing liver disease, pre-existing cardiac disease.

9.2.5 Patient identification code

Each patient will be pseudonymized by using a unique ID which does not contain any information enabling identification of individual patients without access to the source data. The ID consists of a country specific code (e.g. AT or DE), a two-digit site number and a three-digit subject number, starting with 001 at each site.

Sites will be asked to maintain an identification log, see also Section 10.2.

9.2.6 Screening and study visits

The study site is responsible for maintaining an enrolment/screening log that includes all patients screened and enrolled. The log will also serve to document the reason for screening failure. All screening data will be collected and reported in eCRFs, regardless of screening outcome.

Patient visits occur in the course of routine clinical practice. Due to the non-interventional nature of this study, no visit regime is prescribed. The Investigator documents a baseline visit (defined as 1st ropeginterferon alfa-2b administration within the study) and follow-up visits in Part A and Part B for each patient in the eCRF. The eCRF will allow for the documentation of visits as performed according to the management of the individual patient within routine clinical practice.

The subject participation is a maximum of 18 months from enrolment to completion (i.e. last study visit).

The study will include two parts:

Part A:

Part A will be the initial observation phase during the first 6 months of ropeginterferon alfa-2b treatment. Patients receiving ropeginterferon alfa-2b for the first time will be monitored for hepatotoxicity and cardiovascular adverse events.

An interim analysis will be performed after completion of Part A.

[figure not shown]
Part B:

Part B will be the follow-up phase of the initial observation phase (i.e. Part A). Patients will be monitored for hepatotoxicity and cardiovascular adverse events for an additional 12 months.

The effectiveness of risk minimization measures will be evaluated over the entire study period.

The overall study design is illustrated in Figure 1. Details on the procedures to be performed during the study can be found in Table 1 (Section 9.3).

Figure 1. Post-authorisation Safety Study of Ropeginterferon alfa-2b. Part A and Part B of the Study.

9.2.7 Patient withdrawal and patient discontinuation

Any patient may voluntarily withdraw consent for continued participation and data collection. The reason for withdrawal will be recorded on the eCRF page. The data collected on withdrawn patients will be used in the analyses and included in the study report.

Study discontinuation (i.e. complete withdrawal from study participation) may be due to:

- Dropout of the patient (i.e. active discontinuation by patient).
- Patient is lost to follow-up (i.e. discontinuation by patient without notice or action; the Investigator should contact the patient either by telephone or through a clinic visit to establish as completely as possible the reason for the withdrawal.).
- Discontinuation of the patient on Investigator´s discretion if, in his/her judgement, continued participation would pose an unacceptable risk for the patient.

In case the patient discontinues the study (i.e. discontinuation of ropeginterferon alfa-2b treatment), the Investigator should collect and document information on new PV therapy. In case of ropeginterferon alfa-2b treatment discontinuation due to hepatotoxicity, follow-up of the AE as performed in routine clinical practice (e.g. evaluation of hepatic enzymes) should be documented.

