9.10 Other aspects

Not applicable; all aspects of the study are described in the other protocol sections.

10. Protection of human subjects

Due to the non-interventional nature of this study, patients are not exposed to any study-specific medical procedures, and therefore to no study-specific medical risk.

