11.2 Documentation of AEs

All AEs will be collected and recorded in the eCRF over the course of the study from first ropeginterferon alfa-2b exposure to study completion (see section 9.2.2). In case of ropeginterferon alfa-2b treatment discontinuation due to hepatotoxicity, follow-up of the AE as performed in routine clinical practice (e.g. evaluation of hepatic enzymes) should be documented.

- AEs of special interest (as specified in the study protocol section 9.3.1.1), will be documented as solicited AEs.
- For each AE, the Investigator will provide the onset date and time, end date and time, treatment required, outcome, and action taken with the MP (ropeginterferon alfa-2b) and document in the eCRF AE page. It is preferred to use the medical diagnosis, or, if no diagnosis could be established at the time of AE reporting, a symptom or sign, in standard medical terminology in order to avoid the use of vague, ambiguous, or colloquial expressions.
- Each AE will be evaluated by the Investigator for:
 - seriousness
 - intensity
 - causal relationship to medicinal product exposure and
 - relationship to underlying disease PV
- The Investigator must pursue and obtain information adequate to both determine the
 outcome of the AE and to assess whether it meets the criteria for classification as a SAE
 requiring immediate notification to the Sponsor or its designated representative.
- The Investigator must ensure that the follow-up of the patient is appropriate to the nature of the event. Follow up of the patient should continue until resolution of the event or at least stabilization of the patient's clinical status and reported in the eCRF as performed in routine clinical practice.
- If the follow-up of the patient could not be conducted by the Investigator (e.g. patient was transferred to another hospital, etc.), the Investigator will do everything possible to

collect additional information by establishing and maintaining the contact with the person in charge of the patient.

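### Section 9.2.7 equates stopping the drug with leaving the study, so new cardiovascular events and some new hepatobiliary events after a permanent stop have no stated collection

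*Protocol*

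**What the plan says.** Section 9.2.7 introduces its list of reasons with "Study discontinuation (i.e. complete withdrawal from study participation) may be due to". Three reasons follow: active dropout by the patient, loss to follow-up, and the investigator's decision where "continued participation would pose an unacceptable risk for the patient". Stopping ropeginterferon alfa-2b is not one of them. The next paragraph nevertheless treats it as the same thing: "In case the patient discontinues the study (i.e. discontinuation of ropeginterferon alfa-2b treatment), the Investigator should collect and document information on new PV therapy".

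Section 9.2.9 names study discontinuation as one of the reasons for completion and asks for the data available up to that time. Section 11.2 sets the adverse event window as "from first ropeginterferon alfa-2b exposure to study completion". Section 9.2.8 exempts temporary interruptions only.

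The protocol does provide some follow-up after a stop. Section 9.2.7, repeated in Section 11.2, says that "In case of ropeginterferon alfa-2b treatment discontinuation due to hepatotoxicity, follow-up of the AE as performed in routine clinical practice" is to be documented. For adverse events in general, Section 11.2 adds: "Follow up of the patient should continue until resolution of the event or at least stabilization".

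On the endpoint side, Section 9.7.2.2 asks for hepatic and cardiovascular incidences for the whole study as well as, for cardiovascular events, Part A. Section 11.1.1 counts an event as treatment-emergent from the first administration and sets no end date. On risk, Section 10 says that "patients are not exposed to any study-specific medical procedures, and therefore to no study-specific medical risk".

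**The concern.** If a permanent stop ends participation, a patient who stops at month 4 contributes nothing to the cardiovascular incidence from month 4 to month 18, although the endpoint is defined over that period. Patients may stop for reasons linked to their later risk, such as poor control of blood counts or poor tolerance. Observation would then end selectively, and the 18-month incidence of thromboembolic events and MACE, a secondary objective, could be misestimated. Because Section 9.2.7 is inconsistent with itself, sites may also apply it differently: some closing the record at drug stop, others continuing.

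**Working it through.** **What is collected after a permanent stop**

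| Item after the stop | Stated collection | Endpoint that needs it |
|---|---|---|
| The hepatic event that caused a stop for hepatotoxicity | Yes (9.2.7, 11.2), as far as routine practice goes; no duration given | Normalisation and resolution endpoints (9.7.2.4) |
| Any adverse event already recorded | Yes (11.2), to resolution or stabilisation | Already counted |
| New PV therapy | Yes (9.2.7) | Context only |
| New hepatobiliary event after a stop for hepatotoxicity | Not stated | Hepatobiliary events after a stop for liver elevations (9.7.2.4); 9.7.2.2 |
| New hepatobiliary event after a stop for another reason | Not stated | 9.7.2.2; count of patients with hepatobiliary events after an elevation (9.7.2.4) |
| New thromboembolic event or MACE after any stop | Not stated | 9.7.2.2 |

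**Upper bound on the lost observation time**

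Inputs: 228 patients, 20% dropout in one year and 28.5% in 18 months (Section 9.5); 6 + 12 months of observation (Section 9.2.2). Assumptions: a constant dropout hazard, and every dropout is a drug stop.

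1. The protocol's own figure: 1 − 0.8^1.5 = 0.2845, in line with its 28.5%. At 6 months, 1 − 0.8^0.5 = 0.1056, near the 10% in Section 9.9.
2. Hazard: −ln 0.8 = 0.2231 per year.
3. Patients stopped: 228 × 0.2845 ≈ 65 by month 18; 228 × 0.1056 ≈ 24 by month 6.
4. Mean observed time over 18 months: 0.2845 / 0.2231 = 1.275 years.
5. Observed: 228 × 1.275 ≈ 290.6 patient-years. Possible: 228 × 1.5 = 342. Lost: 51.4, or 15%.
6. Part A: possible 228 × 0.5 = 114; observed 228 × 0.1056 / 0.2231 ≈ 107.9; lost 6.1, or 5%.

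**Range under assumptions**

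The documents give neither the share *s* of dropout that is drug stop nor the ratio *R* of the cardiovascular event rate after stopping to that on the drug. Both are assumed here. Other dropout is set aside. With hazard s × 0.2231, off-drug time is 342 − 228 × (1 − e^(−1.5 × s × 0.2231)) / (s × 0.2231), and on-drug time is the remainder of 342. Events unrecorded = R × off / (on + R × off). Recorded rate / true 18-month rate = 342 / (on + R × off).

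| s | Off-drug patient-years | R | Events unrecorded | Recorded / true rate |
|---|---|---|---|---|
| 25% | 13.9 | 1 | 4% | 1.00 |
| 25% | 13.9 | 3 | 11% | 0.92 |
| 50% | 27.1 | 1 | 8% | 1.00 |
| 50% | 27.1 | 3 | 21% | 0.86 |
| 100% | 51.4 | 1 | 15% | 1.00 |
| 100% | 51.4 | 3 | 35% | 0.77 |

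When R = 1, events are missed but a rate per patient-year is not biased. Bias in that rate arises only if risk differs after stopping.

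**The case against.** **An on-treatment scope is legitimate.** Section 9.1 describes both parts as observation during ropeginterferon alfa-2b treatment, and events under a later therapy answer a different question. That is arguable. But the protocol never restricts the incidences to time on treatment, and Sections 9.7.2.2 and 11.1.1 point the other way. Reporting both incidences serves either aim.

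**Section 11.2 may already cover these events.** It refers to Section 9.2.2 for study completion, which there means the end of the whole study. On that reading, adverse events in patients who stopped would still be collected. But Section 9.2.2 does not address drug stop, while Sections 9.2.7 and 9.2.9 close the individual record. The ambiguity is itself a reason to reconcile the sections.

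**Hepatic follow-up exists.** A reader might infer that late hepatic events are lost in the patients most likely to have them. The documents do not support that: a stop for hepatotoxicity carries explicit follow-up. The normalisation and resolution endpoints in Section 9.7.2.4 cover stops for liver elevations or hepatobiliary reactions, which is how Section 9.3.1.1 defines hepatotoxicity. Those endpoints are served. Only new hepatobiliary events remain uncovered.

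**Events that cause a stop are captured.** A vascular event leading to a stop has already happened and can be recorded, and data collected before withdrawal are analysed. This stands: the gap concerns later events only.

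**The unacceptable-risk ground.** A reader might infer that it serves to drop high-risk patients from view. If participation adds no risk, the ground should seldom apply, and nothing shows that it would remove many patients. What stands is a conflict between Sections 9.2.7 and 10. If participation there means treatment, the rule is clinical, and its content is not for this review.

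**Conclusion.** The point holds as a gap in stated data collection. Section 9.2.7 contradicts itself on whether a drug stop ends participation. Read with Sections 9.2.9 and 11.2, it leaves new cardiovascular events, and new hepatobiliary events other than the one that caused a hepatotoxicity stop, without a stated place in the record.

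The 15% of patient-years and the roughly 65 patients are ceilings, not estimates of the effect. They treat every dropout as a drug stop, whereas dropout also includes withdrawal of consent and loss to follow-up, which no rewording recovers. Informative loss is plausible but not demonstrated, because the documents give no figure for risk after stopping. The primary endpoint, confined to Part A, is little affected: about 5% of person-time at most under the protocol's dropout rate. The 18-month secondary endpoints carry most of the exposure. This is a worthwhile, inexpensive correction and does not undermine the study.

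**What to change.** - In Section 9.2.7, define treatment discontinuation and study discontinuation separately, and remove the wording that equates them.
- State that after a permanent stop, unless consent is withdrawn or the patient is lost to follow-up, the site keeps recording from routine records to month 18: hepatobiliary adverse events, available liver values, thromboembolic events, MACE, vital status and new PV therapy.
- Report on-treatment and whole-follow-up incidences side by side.
- Bring Sections 9.2.7, 9.2.9, 9.7.2.2, 9.7.2.4 and 11.2 into line with this.
- Reconcile the unacceptable-risk ground in Section 9.2.7 with the statement of no study-specific risk in Section 10.

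The cost is protocol wording and some extra eCRF entry; no visits or procedures are added. The downside is that some late events will occur under another PV therapy. That therapy is already to be recorded, so such events can be identified and shown separately.
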